2.2 SECONDARY OBJECTIVES

To examine the short and longer term effects on various efficacy and safety measures between a group treated with PEG-IFN monotherapy and an untreated control group, and to evaluate PK in PEG-IFN-treated subjects (see Section 8.1.2), as follows:

Efficacy

- Loss of HBeAg, HBsAg seroconversion (loss of HBsAg and presence of anti-HBs), loss of HBsAg, quantitative serum ALT, proportion of normal ALT, quantitative HBV-DNA, suppression of HBV-DNA < 100,000 copies/mL (< 20,000 IU/mL), < 10,000 copies/mL (< 2,000 IU/mL), undetectable and change from baseline, combined endpoint of HBeAg seroconversion and HBV-DNA < 100,000 copies/mL (< 20,000 IU/mL), and combined endpoint of HBeAg seroconversion and HBV-DNA < 10,000 copies/mL (< 2,000 IU/mL)
- Persistence of HBeAg seroconversion (loss of HBeAg and presence of anti-HBe) over extended long-term follow-up
- Descriptive change from baseline in liver elasticity (in liver elasticity sub-study subjects—see Section 5.3.1.2)

Safety

- AEs (including neurological and psychiatric events), serious and non-serious, and non-serious AEs of special interest
- Laboratory test results (including thyroid function)
- Vital signs (blood pressure, heart rate, temperature)
- Growth: weight and height

Pharmacokinetic

- PK of PEG-IFN following administration of a new BSA-based dosing regimen in PEG-IFN-treated subjects

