HBV DNA ^e	x ^l	x					x	x	x			x		x	x	x	x		x	x	x	x
HBsAg, anti-HBs ^e	x ^l	x					x	x	x			x		x	x	x	x		x	x	x	x
Quantitative HBsAg and HBeAg ^e		x					x	x	x			x				x						
Serum bank ^f		x					x	x	x			x		x	x	x	x		x	x	x	x
RCR plasma & RNA specimen		x					x	x								x	x		x	x	x	x
RCR DNA specimen		x																				
Adverse events		x	x	x	x	x	x	x	x	x	x	x	x	x	x	x	x ^g	x ^g	x ^g	x ^g	x ^g	x ^g
Concomitant medications (including for CHB ^h)	x	x	x	x	x	x	x	x	x	x	x	x	x	x	x	x						
Concomitant medications for CHB only ^h																	x	x	x	x	x	x
Subject study drug diary			x	x	x	x	x	x	x	x	x	x	x									
Dispense study drug		x			x	x	x	x	x	x	x	x										
Compliance			x	x	x	x	x	x	x	x	x	x	x	x	x	x	x	x	x	x	x	x
Neuro-Psychiatric Questionnaire ⁱ	x	x						x		x			x	x								
Liver biopsy	x ^l																					
Liver elastography ^k		x											x			x			x			

^a Or upon and following study treatment withdrawal.

^b By telephone.

^c If there are clinically significant laboratory abnormalities, repeat no less frequently than every 2 weeks or as clinically indicated, with appropriate toxicity management, until they return to normal or baseline values.

Table 2 Schedule of Assessments and Procedures—Group A (PEG-IFN) and Group C (Advanced Fibrotic PEG-IFN) (cont.)

- ^d Specific sites. Blood samples should be collected for PK analysis during Weeks 1 and 24 at pre-dose (0 hour) and 24–48, 72–96, and 168 hours post-dose. Additional pre-dose samples should be collected at Weeks 4, 8, and 12 within 6 hours prior to PEG-IFN administration. The time of PEG-IFN administration on PK sampling days must be recorded on the eCRF.
- ^e Frozen for central processing.
- ^f Sample to be retained frozen at site in the event that any tests need to be repeated. From RCR-consenting subjects, they also may be used for exploratory HBV biomarker analyses (DNA and/or non-DNA). Sample to be retained frozen at site in the event that any tests need to be repeated.
- ^g During the 5-year follow-up period, only persistent AEs initially reported prior to follow-up Week 24, new-onset SAEs *and* non-serious AEs of special interest related to PEG-IFN, and deaths will be collected.
- ^h Concomitant medications for CHB include licensed or investigational immunomodulatory or antiviral therapy, and herbal, botanical and other agents (e.g., ursodeoxycholic acid) that are traditionally used for chronic HBV disease.
- ⁱ Not required for children < 7 years of age.

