	-35 to -1	1	12	24	36	48 ^a	12 ^a	24 ^a	1 ^a	1.5 ^b	2	3	4	5
HBeAg, anti-HBe ^c	x ^j	x	x	x	x	x	x	x	x		x	x	x	x
HBV-DNA ^c	x ^j	x	x	x	x	x	x	x	x		x	x	x	x
HBsAg, anti-HBs ^c	x ^j	x	x	x	x	x	x	x	x		x	x	x	x
Quantitative HBsAg and HBeAg ^{c,j}		x	x	x	x	x		x						
Serum bank ^d		x	x	x	x	x	x	x	x		x	x	x	x
RCR plasma and RNA specimen		x	x	x		x		x	x		x	x	x	x
RCR-DNA specimen		x												
Adverse events		x	x	x	x	x	x	x	x ^e	x ^e	x ^e	x ^e	x ^e	x ^e
Concomitant medications (including for CHB ^f)	x	x	x	x	x	x	x	x						
Concomitant medications for CHB only ^f									x	x	x	x	x	x
Compliance			x	x	x	x	x	x	x	x	x	x	x	x
Neuro-Psychiatric Questionnaire ^g	x	x												
Liver biopsy	x ^h													
Liver elastography ⁱ		x				x		x			x			

^a Eligible subjects may switch at any time between Week 48 and 1 year following Week 48 at which time subjects will continue on the Switch Schedule of Assessments and Procedures.

^b By telephone.

^c Frozen for central processing.

^d Sample to be retained frozen at site in the event that any tests need to be repeated. From RCR-consenting subjects, they also may be used for exploratory HBV biomarker analyses (DNA and/or non-DNA).

^e During the 5-year follow-up period, only persistent AEs initially reported prior to follow-up Week 24 and deaths.

^f Concomitant medications for CHB include licensed or investigational immunomodulatory or antiviral therapy, and herbal, botanical and other agents (e.g., ursodeoxycholic acid) that are traditionally used for chronic HBV disease.

Table 3 Schedule of Assessments and Procedures—Group B (Untreated Control) (cont.)

- ^g Not required for children < 7 years of age.
- ^h Within 2 years prior to baseline or within 9 months prior to baseline for subjects with advanced fibrosis.
- ⁱ Subjects in site-specific liver elasticity sub-study only.
- ^j Parameter does not need to be repeated at re-screening if performed within 6 months prior to baseline, unless dictated by a change in the subject's medical condition or the parameter accounted for the original screen failure.

Table 4 Schedule of Assessments and Procedures—Switch (PEG-IFN)

Assessment/Procedure	Switch BL ^a	Treatment Period (weeks)												Initial Follow-up (weeks Post-End of Principal Observation Period)			Long-Term Follow-Up (years Post-End of Principal Observation Period)					
		SW 1	SW 2	SW 4	SW 8	SW 12	SW 18	SW 24	SW 30	SW 36	SW 42	SW 48 ^b	SW 4 ^b	SW 12 ^b	SW 24 ^b	SW 1 ^b	SW 1.5 ^{b, c}	SW 2 ^b	SW 3 ^b	SW 4 ^b	SW 5 ^b	

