- New-onset SAEs (including neuro-psychiatric events) and non-serious AEs of special interest related to PEG-IFN
- Deaths
- Growth: weight and height
- Thyroid function

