7.2.2 Reporting of Serious Adverse Events (immediately reportable)

Any clinical AE or abnormal laboratory test value that is serious (as defined in Section 7.1.1.3) and that occurs during the study, regardless of the treatment arm, occurring from the enrollment visit (start of study screening procedures), including extended long-term follow-up must be reported to Roche **within 1 working day** of the investigator becoming aware of the event (expedited reporting).

For initial reports of serious adverse events, investigators should record all case details that can be gathered within 1 working day on the Adverse Event eCRF and submit the report via the Electronic Data Capture (EDC) system. A report will be generated and sent to Roche Safety by the EDC system.

In the event that the EDC system is unavailable, a paper Serious Adverse Event CRF and Fax Cover Page should be completed and faxed immediately to Roche Safety. Once the EDC system is available, all information will need to be entered and submitted via the EDC system.

After informed consent/assent, but prior to initiation of study medications, only SAEs caused by a protocol-mandated intervention will be collected (e.g., SAEs related to invasive procedures such as biopsies, medication washout, or no treatment run-in).

After first study drug, all SAEs must be reported.

Unrelated SAEs must be collected and reported during the study treatment/principal observation period and initial 24 weeks of follow-up.

Related SAEs **must** be collected and reported regardless of the time elapsed from the last study drug administration, even if the study has been closed. *Every effort should be made to follow all SAEs considered to be related to the study drug or study-related procedures until a final outcome can be reported.*

Suspected Unexpected Serious Adverse Reactions (SUSARs) are reported to investigators at each site and associated IRB/IEC when the following conditions occur:

- The event must be an SAE.

- There must be a certain degree of probability that the event is an adverse reaction from the administered drug.
- The adverse reaction must be unexpected, that is to say, not foreseen in the SPC text (Summary of Product Characteristics [for an authorized medicinal product]) or the Investigator's Brochure (for an unauthorized medicinal product).

When all subjects at a particular site are off treatment as defined by the protocol:

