8.2.5.3 Safety Data Analysis

The primary safety analysis will compare safety in Group A with Group B *at 24 weeks post-end of treatment/end of untreated observation*. The safety data of Group A and Group B will be qualitatively evaluated alongside subjects in Group C and the switch arm.

- *Incidence, nature, and severity of serious and non-serious AEs (including neurological and psychiatric events)*
- *Reasons for the discontinuation of any study medication*
- *Dose modifications for laboratory abnormalities and clinical AEs*
- *Changes in vital signs and laboratory tests from screening/baseline, including thyroid function*
- *Effect on growth (height and weight)*

The following safety outcome measures will be assessed using descriptive statistics at 1, 2, 3, 4, and 5 years post-end of treatment:

- *Incidence, nature, and severity of persisting AEs, new-onset related SAEs/ non-serious AEs of special interest*
- *Changes in thyroid function from screening/baseline*
- *Effect on growth (height and weight)*

AEs: AEs will be assigned preferred terms and categorized into body systems according to the Medical Dictionary for Regulatory Activities (MedDRA) classification of the World Health Organization (WHO) terminology. Descriptive statistics will be used to summarize safety parameters by group. Neurological and psychiatric AEs will be assessed in further detail, including persistence and duration, as well as new onset of SAEs and non-serious AEs of special interest related to PEG-IFN reported during the extended long-term follow-up period of this study.

Laboratory Safety Data: The laboratory data (including thyroid function) will be analyzed according to Roche's "International Guideline for the Handling and Reporting of Laboratory Data".

Growth (weight and height): The continuous growth will be analyzed with Residual Maximum Likelihood, or analysis of covariance. The assumptions of the analysis such as normally distributed residuals will be assessed. If necessary, rectifying transformations shall be applied. Growth (height) velocity will be explored.

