HBsAg, anti-HBs ^e	x ^l	x					x	x		x		x			x	x	x		x	x	x	x	
Quantitative HBsAg and HBeAg ^e		x					x	x		x		x				x							
Serum bank ^f		x					x	x		x		x			x	x	x		x	x	x	x	
RCR plasma & RNA specimen		x					x	x								x			x	x	x	x	
RCR DNA specimen		x																					
Adverse events		x	x	x	x	x	x	x	x	x	x	x	x	x	x	x	x ^g	x ^g	x ^g	x ^g	x ^g	x ^g	x ^g
Concomitant medications (including for CHB ^h)	x	x	x	x	x	x	x	x	x	x	x	x	x	x	x	x							
Concomitant medications for CHB only ^h																	x	x	x	x	x	x	
Subject study drug diary			x	x	x	x	x	x	x	x	x	x	x										
Dispense study drug		x			x	x	x	x	x	x	x	x											
Compliance			x	x	x	x	x	x	x	x	x	x	x	x	x	x	x	x	x	x	x	x	x
Neuro-Psychiatric Questionnaire ⁱ	x	x					x	x		x		x		x									
Liver biopsy	x ^j																						
Liver elastography ^k		x											x			x							

^a Or upon and following study treatment withdrawal.

^b By telephone.

^c If there are clinically significant laboratory abnormalities, repeat no less frequently than every 2 weeks or as clinically indicated, with appropriate toxicity management, until they return to normal or baseline values.

Table 1 Schedule of Assessments and Procedures—Group A (PEG-IFN) and Group C (Advanced Fibrotic PEG-IFN) (cont.)

- ^d Specific sites. Blood samples should be collected for PK analysis during Weeks 1 and 24 at pre-dose (0 hour) and 24–48, 72–96, and 168 hours post-dose. Additional pre-dose samples should be collected at Weeks 4, 8, and 12 within 6 hours prior to PEG-IFN administration. The time of PEG-IFN administration on PK sampling days must be recorded on the eCRF.
- ^e Frozen for central processing.
- ^f Sample to be retained frozen at site in the event that any tests need to be repeated. From RCR-consenting subjects, they also may be used for exploratory HBV biomarker analyses (DNA and/or non-DNA). Sample to be retained frozen at site in the event that any tests need to be repeated.
- ^g During the 5-year follow-up period, only persistent AEs initially reported prior to follow-up Week 24, new-onset SAEs, non-serious AEs of special interest related to PEG-IFN, and deaths will be collected.
- ^h Concomitant medications for CHB include licensed or investigational immunomodulatory or antiviral therapy, and herbal, botanical and other agents (e.g., ursodeoxycholic acid) that are traditionally used for chronic HBV disease.
- ⁱ Not required for children < 7 years of age.

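### After follow-up Week 24, non-fatal new-onset SAEs have no untreated comparator, and the rules on which SAEs to collect contradict each other

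*Protocol*

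**What the plan says.** **Group B.** Protocol Table 3 footnote e, attached to the adverse-event row for Years 1 to 5, reads "During the 5-year follow-up period, only persistent AEs initially reported prior to follow-up Week 24 and deaths". SAP Appendix 2, Table 2 footnote e is the same.

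**Treated children.** The counterpart footnotes (Protocol Table 2 footnote g for Groups A and C, Table 4 footnote f for Switch) add new-onset SAEs and non-serious AEs of special interest (AESIs). The Protocol joins the two items with *and*, then continues "non-serious AEs of special interest related to PEG-IFN, and deaths will be collected", so the relatedness condition can govern both. The SAP footnotes use a comma list, "new-onset SAEs, non-serious AEs of special interest related to PEG-IFN, and deaths will be collected", in which the condition appears to attach to AESIs only.

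**Protocol text.** Section 5.3.2 lists "New-onset SAEs (including neuro-psychiatric events) and non-serious AEs of special interest related to PEG-IFN" with no distinction by group, and Section 7.2.1 is worded similarly. Section 8.2.5.3 is explicit. Its long-term outcome is "Incidence, nature, and severity of persisting AEs, new-onset related SAEs/ non-serious AEs of special interest", summarised descriptively.

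**Section 7.2.2.** The opening paragraph covers any serious event in any arm, "including extended long-term follow-up must be reported to Roche". A later sentence requires every SAE once study drug has started, with no end date. Another says "Unrelated SAEs must be collected and reported during the study treatment/principal observation period and initial 24 weeks of follow-up".

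**Purpose.** Section 2.2 sets out to examine "short and longer term effects on various efficacy and safety measures between a group treated with PEG-IFN monotherapy" and an untreated control, and lists serious AEs among the measures. SAP Section 2.4 puts long-term safety from Groups A, B and C in the final report.

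**The concern.** The untreated arm supplies the background rate against which events in treated children are read. For non-fatal SAEs that first occur after follow-up Week 24, the schedule removes that rate: Group B shows none whatever happens to those children. In treated children, on the better-supported reading, an event enters the data only if the investigator calls it related. The study is open label (Section 6.4), and Section 7.1.1.2 makes relatedness the investigator's yes/no judgement.

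This can mislead in two directions. Events listed for Group A beside none for Group B may be taken as an excess that the data cannot show. A real excess of events that nobody attributes to the drug would not be recorded. Relatedness is hardest to judge for late or unexpected effects, which long follow-up exists to find.

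There is also a conduct problem. Because the rules disagree, sites may collect differently, and the final dataset would then mix definitions.

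**Working it through.** **Step 1. Apply each rule to one case: a non-fatal hospitalisation first occurring in follow-up Year 3.**

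| Rule | Group B, never treated | Group A, judged unrelated | Group A, judged related |
|---|---|---|---|
| Protocol 7.2.2, opening paragraph | report | report | report |
| Protocol 7.2.2, sentence on SAEs after first study drug | not applicable | report | report |
| Protocol 7.2.2, limit on unrelated SAEs | not required | not required | report |
| Protocol 8.2.5.3 outcome | outside | outside | inside |
| Protocol 5.3.2, 7.2.1 | depends on what *related* governs | depends | report |
| Protocol Table 3, footnote e | not collected | – | – |
| Protocol Table 2, footnote g | – | depends | collect |
| SAP Appendix 2, Table 2, footnote e | not collected | – | – |
| SAP Appendix 2, Table 1, footnote g | – | collect, on the comma reading | collect |

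Only the last column is consistent. The Group B column conflicts between Section 7.2.2's opening and Table 3. The middle column conflicts within Section 7.2.2, and between the SAP footnote and Section 8.2.5.3.

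**Step 2. What both groups still provide.** Table 3 schedules thyroid tests, height and weight for Group B at Years 1, 2, 3, 4 and 5, and footnote e keeps deaths and persisting AEs. The missing control data are new-onset non-fatal SAEs and AESIs.

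**Step 3. Size of the gap.** Arm sizes follow from 145 randomised 2:1: 145 × 2/3 ≈ 97 in Group A and 145 / 3 ≈ 48 in Group B. The 145 reproduces: a two-sided two-proportion calculation for 32% against 10%, with continuity correction, gives 48 controls and 144 in total.

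The documents state no long-term SAE risk, so r is an assumption, taken as equal in both groups. Expected affected children = n × r; under a relatedness filter, n × r × f, where f is the fraction judged related. The chance of at least one affected control = 1 − (1 − r)^48.

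| | r = 2% | r = 5% | r = 10% |
|---|---|---|---|
| Group B, expected if all were collected (48 × r) | 1.0 | 2.4 | 4.8 |
| Chance of at least one in Group B | 62% | 91% | 99% |
| Group B, recorded under footnote e | 0 | 0 | 0 |
| Group A, expected if all were collected (97 × r) | 1.9 | 4.9 | 9.7 |
| Group A, recorded if f = 25% | 0.5 | 1.2 | 2.4 |
| Group A, recorded if f = 50% | 1.0 | 2.4 | 4.9 |
| Group B, expected if half switch (24 × r) | 0.5 | 1.2 | 2.4 |

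**Step 4. What full collection would buy.** With 97 in Group A, the power of Fisher's exact test for 5% (B) against 15% (A) is about 37% with 48 controls and 15% with 24. Collecting all SAEs restores a descriptive background rate, not a formal test.

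**The case against.** The strongest defence is that related-only capture is a deliberate choice, visible in Section 8.2.5.3 and in one sentence of Section 7.2.2. A never-treated child cannot have a PEG-IFN-related event, so Table 3's omission follows. A table labelled as related events should not be read as all-cause incidence. Section 8.2.5.3 places the A-versus-B safety comparison at 24 weeks after treatment or observation and makes Years 1 to 5 descriptive. By then switching has eroded the randomised contrast, and the ban on other anti-HBV treatment in Section 4.4 covers only the period to follow-up Week 24. These points stand and limit the finding.

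It can also be argued that the opening of Section 7.2.2 sets only the reporting deadline and the later sentences set the scope. That does not remove the conflict. The opening itself names the arms and periods covered, and the sentence on SAEs after first study drug has no end date.

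Three stronger readings are tempting but unsupported:

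- A reader might infer that long-term safety follow-up has no usable control data. Step 2 shows otherwise.
- A reader might infer that no serious event in an untreated child is captured. Fatal events are recorded as deaths, events that began before follow-up Week 24 and persist are recorded, and Section 7.2.2's opening would capture the rest if it governs.
- A reader might put a significance test on Group A events against a Group B zero and speak of a false finding of harm. Neither document plans that test. The result would need an assumed risk, nearly all Group A events judged related, and no switching.

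**Conclusion.** The point holds in a limited form. After follow-up Week 24, non-fatal new-onset SAEs and AESIs have no untreated comparator under the schedule. The SAEs that enter the data for treated children depend, on the better-supported reading, on an unblinded relatedness judgement. That reading is not uniform, because the SAP footnotes do not clearly carry the condition. Section 7.2.2 contradicts both itself and Table 3.

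Only this part of the Section 2.2 longer-term safety objective is affected. The primary efficacy analysis and the 24-week safety comparison are untouched.

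At an assumed risk of 2% to 10%, about 1 to 5 affected children among 48 controls would go unrecorded, and fewer to the extent that controls switch. These counts assume equal risk in both groups and no loss to follow-up. The textual conflict needs no assumption. It should be corrected, because the long-term report could otherwise invite a comparison that its data cannot support.

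**What to change.** Choose one collection rule for the period after follow-up Week 24 and use it throughout: Protocol Sections 5.3.2, 7.2.1, 7.2.2 and 8.2.5.3, the synopsis, the footnotes to Tables 2 to 4, and the SAP's synopsis copy and schedule footnotes.

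The preferred rule is to record every new-onset SAE in every group at the annual contacts already scheduled, with relatedness as a recorded attribute and not a condition for entry. Table 3 already has an adverse-event entry at each of those contacts. The footnotes should also state whether AESIs apply to Group B. The cost is a small amendment and some extra SAE data entry, with no new visit or procedure. The gain is a descriptive comparator, reduced by switching.

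If that is not accepted, keep the related-only rule, remove the conflicting sentences, and state in Section 2.2 and SAP Section 2.4 that long-term new-onset SAE and AESI data cover PEG-IFN-treated children only, with no between-group statement made on them.
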